2.5. Secondary Variable(s)

2.5.1. Phase I

2.5.1.1. PK of hu3F8-BsAb

See section 6.8 for more details

2.5.1.2. HAHA

Blood (~5ml per draw) drawn before each cycle for HAHA testing will be measured using ELISA. Antiidiotype antibodies (Ab3, Ab3') will be also tested with the same blood samples. This blood sample may also be tested for HAMA. HAMA positivity is allowed and will not affect patients' eligibility for treatment.

2.5.1.3. ORR

For NB, anti-tumor activity will be measured by revised INRC.

For osteosarcoma and other GD2(+) tumors, the response and progression will be evaluated in this trial using the RECIST Committee, version 1.1.

The proportion of NB, osteosarcoma, and other GD2(+) tumor patients responding to therapy will be determined for each disease type.

ORR will be defined as the proportion of patients achieving CR or PR as BOR at the end of cycle 4.

In addition, a similar analysis will be performed corresponding to end of trial but before any new prohibited anticancer therapy intakes. Potential response assessments after initiation of any new prohibited anticancer treatment will not be included in the assessment of BOR.

Thus, the BOR will be the best response recorded from the initiation to the following timepoints:

- At the end of cycle 4
- At the end of the trial.

For patients with osteosarcoma and other GD2(+) tumors, each patient will be assigned one of the following categories: CR, PR, Stable Disease, Progressive Disease, Not Evaluable (NE).

Patients' response will also be classified as "unknown" if insufficient data were collected to allow evaluation per these criteria.

According to RECIST v1.1, the following table provides a summary of the overall response status calculation at each time point for patients with or without measurable disease at baseline:

Target Lesions	Non-Target Lesions	New Lesions	Overall Response
CR	CR	No	CR
CR	Non-CR/Non-Progressive Disease	No	PR
CR	Not all evaluated	No	PR
PR	Non-Progressive Disease / not all evaluated	No	PR
Stable Disease	Non-Progressive Disease / not all evaluated	No	Stable Disease
Not all evaluated	Non-Progressive Disease	No	NE
Progressive Disease	Any	Any	Progressive Disease
Any	Progressive Disease	Any	Progressive Disease
Any	Any	Yes	Progressive Disease

Table 4 Integration of target, non-target and new lesions into response assessment

Note: Patients with a global deterioration of health status requiring discontinuation of treatment without objective evidence of disease progression (or evidence of unequivocal disease progression) at that time should be reported as "*symptomatic deterioration*". This is a reason for stopping therapy, but is NOT objective Progressive Disease. Every effort should be made to document the objective progression even after discontinuation of treatment.

The overall response will be determined for all protocol specified assessments, ie scheduled assessments (with or without missing information) and also for all unscheduled assessments with non-missing information.

If a scheduled assessment is completely missing (target, non-target, new lesion), the overall response will be NE.

When Stable Disease is believed to be the BOR, it needs to be assessed a minimum of 6 weeks (+/- 7 days) after start of treatment. Otherwise, the BOR will be NE, unless any Progressive Disease was further documented, in which case BOR will be Progressive Disease.

If a patient progressed before this first assessment, he will be considered as 'early progressive'. If this event occurs, the overall response of the patient will be presumed as progression. This corresponds to patient who withdraws without any scan and whose reason for ending treatment or ending study is progressive disease (according to investigator opinion). In case of patient with a reason different to progressive disease, he will not be considered as progressive disease but will be at least considered as non-responder.

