9 TREATMENT/INTERVENTION PLAN

- 9.1 Phase I
- 9.1.1 General Outline

During phase I approximately 0.5 ml of the first Bs-Ab infusion will be collected about half-way through the infusion and assayed in Neuroblastoma research laboratory to determine quantity of hu3F8-BsAb in the final infusion product. In cycle 1, blood is drawn for PK studies as described in Section 9.1.4. Patients are admitted for dose 1 of cycle 1 of treatment and will be inpatient for approximately 4 days (minimum 48 hours) though the duration of stay may change if clinically indicated. Subsequent doses can be administered inpatient or outpatient. Patients are monitored for DLT clinically with physical examination, CBC and complete chemistry until Day 28. Patients with DLT will come off treatment HAHA titer is measured after each cycle. HAHA draws require about 5mL of serum. If HAHA develops, cycles are deferred for up to 4 months until HAHA titer until <1300 U/ml. Extent of disease evaluation will be performed after the second dose of hu3F8-BsAb in cycle 2 and cycle 4, every 3 months thereafter. (Table 6) A total of 4 cycles will be given.

Patients with no life-threatening toxicity clearly attributable to hu3F8-BsAb, no PD, and continuing to meet all eligibility criteria (with subsequently explained exceptions) have the option of receiving additional cycles up to 2 years from the start of the hu3F8-BsAb treatment. Inclusion criteria that no longer apply for patients to receive subsequent cycles are: disease status, since patients achieving remission may continue; and prior T cell immunotherapy timing restrictions, since all patients will have received Cycle 1 of hu3F8-BsAb. Even patients who achieve remission may continue therapy beyond

4 cycles. DLT and dose-schedule are described in Section 9.1.2 and 9.1.3. After cycle 2, intra-patient dose escalation will be permitted i.e. patients can receive the highest dose that has been evaluated and proven safe by DLT assessment. Patients will be admitted for at least 48 hours for their first escalated dose.

The treatment and evaluation schedule may require minor adjustment as clinically indicated or due to circumstance (e.g. due to PDH closure for holidays or due to inclement weather).

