13 CRITERIA FOR REMOVAL FROM STUDY

- **13.1** Patients come off treatment if there is PD at any time. Best clinical judgment will be used to determine whether a patient must undergo tests between cycles to make sure disease is not progressing. Patients are followed for toxicities for 30 days from last treatment.
- 13.2 Patients come off treatment if they have DLT (during cycle 1 of phase I) or life-threatening toxicity clearly attributable to hu3F8-BsAb. Patients in the first stage of phase I (one patient per dose level cohort) who experience ≤ grade 2 toxicity, will not come off treatment but can continue at the same dose if they do not experience DLT and if toxicity subsides to <grade 2 within 35 days of dose 1 of Hu3F8-BsAb.

- **13.3** Patients who become pregnant during the study must be withdrawn from treatment
- **13.4** The investigators will make every reasonable effort to keep each patient in the study until all planned treatments and assessments have been performed. The investigators may discontinue study drug treatment for the following reasons:
 - Adverse events, including unacceptable toxicity or exacerbation of underlying disease, associated with study drug administration and necessitating discontinuation of treatment. Patients who are coming off treatment due to adverse events will be treated and followed according to established, acceptable medical practice. All pertinent information concerning the outcome of such treatment will be entered in the MSKCC institutional Clinical Research Database (CRBD). Patients will be followed until resolution or stabilization of the adverse event.

13.5 Off Study Criteria:

- Thirty days after the last dose of study drug for patients coming off treatment due to DP
- For patients coming off treatment due to adverse events, patients will be followed until the date the event returns to baseline or <Grade 3 (whichever is higher) or the date patients start another treatment, whichever is earlier.
- Death
- Lost to follow-up
- Withdrawal of consent. The patient's desire to withdraw from the study may occur at any time. The investigator should carefully consider whether the patient's withdrawal of consent is due to an adverse event, and if so, record the adverse event as the reason for withdrawal.
- Withdrawal by the physician for clinical reasons not related to study drug treatment in the absence of an adverse event.

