2.1.1. Phase I

2.1.1.1. Phase I Design

Initially the phase I trial will follow a dose-escalation schema with 1 patient assigned per dose until the first \geq Grade 2 toxicity (except for Grade 2 sinus bradycardia, sinus tachycardia, urticaria, fever, nausea, vomiting, diarrhea, urticaria, headache, paresthesia, electrolyte disturbances, pain) is observed, then the subsequent dose allocation will follow the Continual Reassessment Method (CRM)^{1,2}. Eligible patients will include relapsed or refractory NB, osteosarcoma, and GD2 (+) solid tumors. In each cycle, hu3F8-BsAb is given on Days 1 and 8. PK is assessed by blood draws. Patients are monitored for Dose Limiting Toxicity (DLT) until Day 28. Patients with DLT will come off treatment. Human Anti-Human Antibody (HAHA) titer will be measured after each cycle. Extent of disease evaluation will be performed after the second dose of cycle 2 and cycle 4, then every 3 months thereafter. A total of 4 cycles will be given.

If patients experience no life-threatening toxicity clearly attributable to hu3F8-BsAb, do not develop progression of disease and continue to meet all eligibility criteria, they have the option of receiving additional cycles up to 2 years from the start of hu3F8-BsAb treatment. Patients may continue therapy beyond 4 cycles even if they achieve remission (see Figure 1). The duration of each subsequent cycle is 28 days with hu3F8-BsAb being given on Days 1 and 8. MTD is defined as the dose level that leads to DLT in approximately 15% of patients (posterior probability of DLT that comes closest to the toxicity level of 0.15). The RP2D will be decided based on the safety data in the phase I and can be MTD or lower. If MTD is not reached, RP2D may be determined on the basis of PK studies. If no DLT is observed, the RP2D will be determined as a minimum dose that gives the highest hu3F8-BsAb serum levels based on the PK data. For example, the RP2D of hu3F8 monoclonal antibody was decided as 9 mg/kg/cycle because the serum hu3F8 levels reached a plateau beyond 8.4 mg/kg/cycle with no DLT (see Protocol Section 3.2.3). After cycle 2, intra-patient dose escalation will be permitted i.e. patients can receive the highest dose that has been evaluated and proven safe by DLT assessment.

Figure 1 Trial Design

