4	Hu3F8-BsAb 2.6 mcg/kg/cycle	2.6 mcg/kg
5	Hu3F8-BsAb 4.8 mcg/kg/cycle	4.8 mcg/kg
6	Hu3F8-BsAb 9.3 mcg/kg/cycle	9.3 mcg/kg
7	Hu3F8-BsAb 21.3 mcg/kg/cycle	21.3 mcg/kg
8	Hu3F8-BsAb 41.3 mcg/kg/cycle	41.3 mcg/kg
9	Hu3F8-BsAb 81.3 mcg/kg/cycle	81.3 mcg/kg
10	Hu3F8-BsAb 161.3 mcg/kg/cycle	161.3 mcg/kg
11	Hu3F8-BsAb 301.3 mcg/kg/cycle	301.3 mcg/kg
12	Hu3F8-BsAb 501.3 mcg/kg/cycle	501.3 mcg/kg

Table 5 Treatment Labels for Phase I

If dose is changed after cycle 2 in phase I, tumor response will be evaluated based on the combination of the doses. Thus, some additional columns may be added.

Table 6 Treatment Labels for Phase II

Ordering	Full treatment group (a minima for	Short format labels (for use when
	listings)	space is limited) for tables
13	Hu3F8-BsAb RP2D Group 1	Hu3F8-BsAb RP2D NB
	(Neuroblastoma)	
14	Hu3F8-BsAb RP2D Group 2	Hu3F8-BsAb RP2D OS
	(Osteosarcoma)	
15	Hu3F8-BsAb RP2D Overall	Hu3F8-BsAb RP2D Overall

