6.6.3. Secondary Efficacy Analysis

6.6.3.1. ORR for Phase I

ORR for patients from phase I will be estimated for each disease type (excluding potential response assessments after initiation of any new prohibited anticancer treatment) and provided

Final, Version 1.0, 06Oct2021

with 90% and 95% two-sided Confidence Intervals using Wilson's method, by treatment group in the FAS.

For NB, anti-tumor activity will be measured by revised INRC, as described in section 2.4.2.1.

For osteosarcoma and other GD2(+) tumors, the response and progression will be evaluated in this trial using the RECIST Committee, version 1.1. as described in Section 2.5.1.3. The proportion of NB, osteosarcoma, and other GD2(+) tumor patients responding to therapy will be determined for each disease type.

In addition, overall response at each cycle excluding potential response assessments after initiation of any new prohibited anticancer treatment will be provided with the two-sided 90% and 95% confidence intervals using the Wilson's method.

Swimmer plot will also be produced (split by disease type if needed) with the following characteristics:

- Responses at each cycle over time for X axis starting from the first treatment date
- Dose levels and patient numbers for the Y axis.

Patients whose CRF response is "Very Good Partial Response" will be considered as "Partial Response" for the analyses.

ORR values will be also presented in a data listing as well as overall responses at each cycle.

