6.7.8.2. Phase I Analysis

As described above, at the end of Phase I, all efficacy and safety analyses corresponding to phase I as well as PK analyses will be performed in order to let DMC members provide recommendation regarding the MTD and RP2D to be selected for Phase II.

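### Phase I response is counted from first dose but can be tabulated by the dose combination later received, which can make escalated columns look more active with no dose effect

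*SAP*

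**What the plan says.** Four rules bear on this point.

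- **Counting window.** SAP 2.5.1.3 defines Phase I best overall response (BOR) from the start of treatment: "Thus, the BOR will be the best response recorded from the initiation to the following timepoints". The two timepoints are the end of cycle 4 and the end of the trial.
- **Grouping.** SAP 6.1, under the Phase I treatment labels, says "If dose is changed after cycle 2 in phase I, tumor response will be evaluated based on the combination of the doses", and adds "Thus, some additional columns may be added". SAP 6.6.3.1 gives Phase I ORR for each disease type with Wilson intervals, "by treatment group in the FAS"; the FAS is all treated patients. SAP 6.6.6.6 does the same for disease control rate (DCR).
- **Who can change dose.** Protocol 9.1.1 says "After cycle 2, intra-patient dose escalation will be permitted", and Protocol 13.1 says "Patients come off treatment if there is PD at any time". SAP 2.1.1.1 sets the scan schedule: "Extent of disease evaluation will be performed after the second dose of cycle 2 and cycle 4, then every 3 months thereafter".
- **Use.** SAP 6.7.8.2 says that at the end of Phase I "all efficacy and safety analyses corresponding to phase I as well as PK analyses will be performed", so that the DMC can recommend the MTD and RP2D.

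The SAP states grouping by originally assigned dose only for the by-patient DLT listing (SAP 6.7.2). For response it gives no such table, no landmark, and no restart of the response window at the dose change.

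**The concern.** The response clock starts at first dose, but membership of an escalated combination is settled no earlier than the start of cycle 3. Patients who progress or stop before then can appear only under their starting dose. Patients who last longer can move to a combination and take with them any response already seen on the lower dose. This is guarantee-time (immortal-time) bias. Its direction is fixed: under no dose effect it favours the escalated columns. The DMC would see these tables alongside the safety and PK data, and they could suggest that higher doses are active and lower ones are not.

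**Working it through.** The documents give no Phase I response, drop-out or escalation rate, so there is no stated figure to reproduce. The check is the order of events, followed by an illustration.

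**Order of events.** With 28-day cycles, the second dose of cycle 2 falls nominally on day 28 + 8 = 36, and cycle 3 Day 1 on day 1 + 2 × 28 = 57. The first disease evaluation is due after the former. The first possible escalated dose comes at the latter. A Cycle 2 response can therefore precede any higher dose and still count in BOR for the combination.

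**Illustration.** Let r be the true ORR at every dose, q the share progressing or otherwise off treatment before cycle 3, and e the share of continuing patients who escalate. All three are assumptions. Assume also that responders come only from continuing patients, that escalation is independent of response, that all escalated patients are pooled, and that escalated patients leave their starting-dose column.

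- Escalated ORR = r / (1 − q)
- Non-escalated ORR = r(1 − e) / [q + (1 − q)(1 − e)]

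With r = 0.20 and q = 0.50:

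| e | Escalated | Non-escalated |
|---|---|---|
| 0.50 | 0.20/0.50 = 40% | 0.10/0.75 = 13% |
| 0.80 | 0.20/0.50 = 40% | 0.04/0.60 = 7% |

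As a check at e = 0.50, escalated patients are 25% of the total, and 0.25 × 40% + 0.75 × 13.3% = 20%, the true rate.

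**Range.** Over r = 10–30%, q = 40–60% and e = 50–80%:

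- The escalated group runs from 0.10/0.60 = 17% to 0.30/0.40 = 75%.
- The non-escalated group runs from 0.02/0.68 = 3% to 0.15/0.70 = 21%.

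**Other groupings, same assumptions.** By initially assigned dose, the expected ORR is r = 20% in every column. Among patients still continuing at cycle 3, escalated and non-escalated groups both have r/(1 − q) = 40%. The gap comes from the grouping, not from dose.

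**The case against.** Five objections deserve weight.

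1. **The column rule is not firm.** Evaluation by combination is stated as planned, but extra columns only may be added. The SAP does not say that escalated patients leave their starting-dose column, and layout is left to table shells that are not part of these documents. This stands, so the conclusion is conditional. If the assigned-dose column is kept whole, it is not depleted, but the combination column is still a selected group: 40% against 20% in the illustration.

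2. **Nothing is fixed by construction.** A reader might infer that escalated columns hold only patients who were progression-free at the Cycle 2 scan, so that they show no Cycle 2 progression and a DCR of 100%. The documents do not support that. SAP 5.1.4 sets the Cycle 2 scan window at day 61 ± 30, that is days 31 to 91, so the scan can fall after nominal day 57. Protocol 12.5 lets suspected pseudoprogression be followed for about 4 weeks. SAP 2.5.1.3 scores a wholly missing scheduled assessment as not evaluable. The supportable condition is being on treatment without recognised progression when cycle 3 starts.

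3. **The dose decision does not rest on ORR.** A reader might infer that the artefact would select the RP2D. Protocol 4.1.1 and SAP 2.1.1.1 base the RP2D on safety data, or on PK when the MTD is not reached or no DLT occurs. SAP 6.7.2 takes the MTD from the CRM and other safety data. No formal dose-response test of ORR is planned. Efficacy results are supplied to the DMC, and that is as far as the text goes.

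4. **The illustration pools what the SAP splits.** About 30 patients are spread over 12 levels and three disease categories, so most cells will hold few patients and have wide intervals. The percentages show direction and possible size; they do not forecast any planned cell.

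5. **Some safeguards exist.** SAP 6.6.3.1 plans response at each cycle, a listing, and a swimmer plot over time. These would help a careful reader to date a response, but they do not correct a rate shown by combination.

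**Conclusion.** The concern holds in conditional form. Counting BOR from first dose while grouping by the dose combination later received is open to guarantee-time bias, and nothing in SAP 2.5.1.3, 6.1 or 6.6.3.1 removes it. If combination columns replace the assigned-dose column, ORR and DCR can be higher in escalated than in non-escalated columns with no dose effect. The illustrative size of 40% against 13% or 7% depends wholly on the assumed rates and on pooling. The contrast is between escalated and non-escalated patients; it is not a graded dose-response. The tables go to the DMC but are not a stated basis for the RP2D. The wording should be corrected before the Phase I tables are produced; the point does not invalidate dose selection.

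**What to change.** In SAP 6.1, 6.6.3.1 and 6.6.6.6:

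- Make the main Phase I tables of ORR, DCR and response by cycle by initially assigned dose level, for all FAS patients, with the number escalated shown in each column.
- Use the Cycle 2 response by assigned level as the dose-response summary. Restrict it to assessments made before any dose change, and show how many patients have none.
- Keep dose-combination results only as a descriptive listing, or in the planned swimmer plot with the dose at each assessment marked. Limit them to responses first seen after the dose change, and do not compare them with other columns.

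The definition of BOR in SAP 2.5.1.3 can stay. The cost is SAP text and table shells; no new data, sample size or treatment rule is involved. There is one small downside: BOR by assigned level credits responses first reached after escalation to the starting dose. This matters most for the end-of-trial version, since treatment can run up to 2 years. Those responses must therefore be flagged in the table.

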2.5.1.4. PFS

PFS is defined, like primary endpoint of Group 2 of phase II, at the time from first dose of treatment to the date of first progression or death from any cause, whichever occurs first.

Same censoring rules as those used for Group 2 of phase II will be applied considering INRC assessments instead of RECIST v1.1 assessments for NB patients.

PFS (in months) will be computed as [date of event or censoring – First dose of treatment + 1]/30.4375.

PFS will be calculated with one decimal.

2.5.1.5. OS

OS will be defined as the time from the first dose of treatment to the time of death or last follow up known to be alive for patient without death date.

For patients who have not died, overall survival will be censored at the date of last contact (date the patient was last known to be alive).

OS (in months) = [date of event or censoring – First dose of treatment + 1]/30.4375.

OS will be calculated with one decimal.

2.5.2. Phase II

2.5.2.1. Duration of Complete Remission

Duration of CR is defined only for patients who achieve CR after hu3F8-BsAb and will be calculated from the time of remission to the date of progression or death, whichever occurs first.

Same censoring rules as for PFS will be applied for CR duration analysis (See section 2.4.2.2).

CR duration (in months) will be computed as [date of progression or death or censoring – CR date + 1]/30.4375.

CR duration will be calculated with one decimal.

2.5.2.2. ORR for Group 2

ORR will be defined as the proportion of patients achieving CR or PR based on RECIST v1.1 as the best response at the end of cycle 4 (excluding potential response assessments after initiation of any new prohibited anticancer treatment).

2.5.2.3. HAHA

HAHA will be measured as described for phase I (section 2.5.1.2).

2.6. Exploratory Efficacy Variable(s)

2.6.1. Phase II

2.6.1.1. Overall Survival (OS)

OS will be defined as the time from the first dose of treatment to the time of death or last follow up known to be alive for patient without death date.

For patients who have not died, overall survival will be censored at the date of last contact (date the patient was last known to be alive).

OS (in months) = [date of event or censoring – First dose of treatment + 1]/30.4375.

OS will be calculated with one decimal.

